Hypothesis #1B: *Whole blood resuscitation will be associated with a lower incidence of 12 hour and 24 hour mortality, a lower incidence of death from exsanguination, incidence of MOF, nosocomial infection, improved transfusion ratios, lower overall blood transfusion requirements and shorter time to hemostasis as compared to those resuscitated with component therapy.*

Hypothesis #1C: *Whole blood resuscitation will be associated with an improved Glasgow Outcome Score-Extended at 6 months post injury as compared to those resuscitated with component therapy in patients with traumatic brain injury.*

Hypothesis #2A: *A nadir prehospital and acute phase resuscitation systolic blood pressure greater than or equal to 120 mmHg will be associated with improved traumatic brain injury outcomes at discharge and at 6 months.*

Linking Investigations in Trauma and Emergency Services

Task Order 2: Shock, Whole blood and Assessment of TBI (SWAT)

Hypothesis #2B: *The magnitude of the dose depth curve of systolic blood pressure during the prehospital and acute phase resuscitation will be associated with neurological outcome differences at discharge and at 6 months following traumatic brain injury.*

Research Design and Methods

Study Design: The LITES Network will perform a multicenter, prospective, observational cohort study over a 4 year period to determine the impact of whole blood resuscitation in trauma patients with hemorrhagic shock at risk of large volume resuscitation with and without TBI. Early whole blood resuscitation will be compared to standard component resuscitation. The study will also further characterize blood pressure and resuscitation endpoints in poly-trauma patients with traumatic brain injury. Six trauma sites with appropriate characteristics will be selected from network sites across the country. (Figure 2)

Figure 2

Study Setting: The study will be performed utilizing busy level I trauma centers from within the LITES Network located across the country, at sites where either whole blood has currently been incorporated into standard of care or where component blood transfusion is being utilized for patients in hemorrhagic shock at risk for large volume resuscitation. Due to the paucity of trauma centers who are currently utilizing whole blood for trauma patients as standard of care, the potential to incorporate additional sites may be required over time.

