same to research personnel. If obtaining informed consent is not feasible and a legally authorized representative is not reasonably available, the informed consent will be sent via trackable means. The letter will be sent via trackable means and documentation of the addressee and date of mailing and the delivery confirmation with will be kept in the study folder. The subject or their LAR will return the consent using a study provided postage paid envelope. If a signed consent document is not obtained, ~~we don't receive any signed~~ no research activities will be performed nor data will be extracted from the medical record, beyond 36 hours period covered by the Waivers of Consent and HIPAA. Samples and data acquired under those Waivers will be retained.

Whole Blood Transfusion Sites: Busy, Level 1 trauma centers from within the LITES Network will be selected based upon the ability to enroll patients with the proposed inclusion and exclusion criteria who have already implemented or are in the direct process of implementing an urgent release whole blood resuscitation protocol and are able to perform all necessary requirements for the planned prospective cohort study proposed. Those sites with the capabilities to deliver at least 4 units of WB will be selected for participation with preference given to ≥ 6 units urgent release WB capabilities. WB sites will be selected based upon the ability to enroll 33% of patients for the overall cohort study. As WB resuscitation becomes increasingly more widely adopted, there exists the potential to include additional WB sites from within the network as respective institutional practice changes over the 4 year time point of the study. Similarly, there exists the potential to incorporate additional trauma sites into the LITES network based upon their abilities to enroll poly-trauma patients in hemorrhagic shock and the utilization of WB resuscitation. As different trauma sites may utilize differing WB products with different titer levels, matching processes, and leukocyte reducing capabilities, these WB characteristics will be documented for all sites and for all WB units and respective patients enrolled.

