Sample Tracking, Management and Storage: After sample obtainment, processing and storage, samples will initially be batched sent to the University of Pittsburgh biological sample repository where it will be tracked, managed and stored until the necessary translational or mechanistic measurement are performed. The CCC and DCC have a long track record of coordinating such processes.

Power Analysis: The prospective cohort study will utilize time to 4 hour mortality for its primary outcome to power the study. Based upon the 6 LITES Network sites admission history that will be utilized and their respective volume of hemorrhagic shock patients meeting inclusion and exclusion criteria and a 3.5 year enrollment time period, we plan to initiate sampling on 1,050 patients over the enrollment time period of the study. With an 85% consent rate which is an estimate based upon prior studies of similar nature, we will consent for participation 892 patients for the study. With an estimate baseline rate of 4 hour mortality of 11.1 % derived from the PROPPR study, there will be 90% power to detect a hazard ratio of 1.9.

Calculations are based on the primary aim of the study based on the following assumptions:

- Type I error rate of 0.05
- Two-sided alternative hypothesis

Linking Investigations in Trauma and Emergency Services

Task Order 2: Shock, Whole blood and Assessment of TBI (SWAT)

- 6 sites will be involved, three whole blood and three component sites
- Each site will enroll 175 participants in 3.5 years of enrollment, of which, 85% will be eligible for the study (149)
- The calculations are based on Cox proportional hazard model
- A 4 hour event rate in the control (non-whole blood) group of 0.111

The power calculations for these secondary aims are presented below. When reporting the results of the analyses, caution will need to be taken with respect to the interpretation of the findings since they are secondary in nature.

The secondary outcomes in Aim 1B include binary outcome, continuous outcomes, and time to event outcomes. For the binary outcomes, the odds ratio that can be detected is presented in Table 1. For the continuous outcome, the effect size that can be detected is 0.13. Finally, for the time to event outcomes, the hazard ratio that can be detected over a range of event rates in the control group is also presented in Table 1.

Event Rate	.1	.2	.3	.4	.5	.6
Odds Ratio	1.76	1.56	1.49	1.46	1.46	1.48
Hazard Rate	2.69	1.70	.37	.30	.27	.30

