- For Aim 1C, a nonparametric analysis of variance will be used to compare the distribution of the GOS-E between the two groups. An effect size of 0.17 could be detected.
- For aim 2A, a nonparametric analysis of variance will be used to compare the distribution of the GOS-E between the two groups. An effect size of 0.28 could be detected.
- For aim 2B, a nonparametric correlation coefficient will be used to assess the association between GOS-E and the area under the systolic blood pressure curve. For each, a 95% confidence interval with a width of 0.19 can be estimated.
- For all secondary analyses, the type I error rate was set to 0.05, with a two-sided alternative hypothesis, and 90% power. For the Aim 1, the sample size will be 1,190. For Aim 2, the sample size will be limited to those with a traumatic brain injury. For the purposes of this study, this is expected to be 35% or a total of 417 participants.

Analyses

AIM#1: The analysis will begin by describing the baseline demographic and clinical characteristics of the overall population and then stratified by whole blood usage. The characteristics will be

Linking Investigations in Trauma and Emergency Services

Task Order 2: Shock, Whole blood and Assessment of TBI (SWAT)

compared among those who receive and who do not receive whole blood. For discrete variables, proportions will be generated and a chi-square test will be used to test for differences between the proportions. For continuous characteristics, means (medians) and standard deviations (interquartile ranges) will be calculated and t-tests (Wilcoxon) will be used to compare the means (distributions) among those who receive and do not receive whole blood.

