Hypothesis#1A: For the primary outcome, the time to death will be generated for each participant. Kaplan-Meier curves will be generated for each treatment group and a log-rank test will be used to compare the distribution of the cumulative proportion. A hierarchical Cox-proportional hazards regression model will be used to control for the within-institution clustering. The hierarchical Cox-proportional hazards regression model will then be used to assess the independent impact of whole blood on time to death after controlling for the clustering effect and potential confounding effects of baseline characteristics. The model will include main effects for whole blood usage and a propensity score for receiving whole blood. The propensity score for the use of whole blood will be generated using a boosted logistic regression model. The dependent variable in the model will be the use of whole blood and the independent variables will be the baseline characteristics of the population. The Cox-proportional hazards model will be used to estimate the cumulative probability of death 4 hours.

Hypothesis#1B: The analytic approach for the secondary outcomes included in Hypothesis#1B will vary based on the type of outcome. For binary outcomes (e.g., 12 hour and 24 hour mortality, death from exsanguination, incidence of MOF, nosocomial infection), the same analytic approach that was carried out for Hypothesis 1a will be implemented.

For continuous outcomes (e.g., transfusion ratios, blood transfusion requirements) a two-sided t-test for correlated means will be used to compare the means between those receiving and not receiving whole blood. A hierarchical analysis of variance model will be used to control for the within-institution clustering. The model will be used to assess the independent impact of whole blood after controlling for the clustering effect and the potential confounding. The model will include main effects for whole blood usage and propensity for receiving whole blood.

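### The stated 90% power for a hazard ratio of 1.9 lists no allowance for within-site correlation, so it is unsupported for the planned hierarchical Cox analysis; the size of the loss cannot be fixed from the documents

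*Combined protocol and SAP*

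**What the plan says.** The Power Analysis section plans for 892 consented patients and states that "there will be 90% power to detect a hazard ratio of 1.9". Its assumptions are a two-sided 5% type I error, six sites of 149 analysed patients, and these two:

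- "The calculations are based on Cox proportional hazard model"
- "A 4 hour event rate in the control (non-whole blood) group of 0.111"

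On site type it says "6 sites will be involved, three whole blood and three component sites". Study Setting explains how sites come in: "at sites where either whole blood has currently been incorporated into standard of care or where component blood transfusion is being utilized". The Whole Blood Transfusion Sites section gives a different share: "WB sites will be selected based upon the ability to enroll 33% of patients for the overall cohort study".

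The comparison itself is by receipt. Under Analyses, AIM#1, characteristics are "compared among those who receive and who do not receive whole blood". For the primary outcome, Hypothesis#1A first says "a log-rank test will be used to compare the distribution of the cumulative proportion". It then moves to a hierarchical Cox model for institutional clustering, and to that model with a propensity score for receiving whole blood.

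**The concern.** When sites are recruited for their blood practice, part of the whole-blood contrast is a contrast between sites. Patients at one site share surgeons, transport times, case mix and transfusion protocols, so their early mortality may be correlated. With about 149 patients per site, even a small ICC inflates the variance of a between-site contrast. The analysis plan recognises this by specifying a hierarchical model; the list of power assumptions does not.

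At stake is how a null or imprecise result is read. A reader who trusts 90% power may take a non-significant hazard ratio as evidence against a 1.9-fold effect, when the study may have had much less power to see one.

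**Working it through.** **Inputs from the documents.** N = 892 (1,050 × 0.85 = 892.5); 149 per site (6 × 149 = 894); 11.1% mortality at 4 hours; hazard ratio (HR) 1.9; two-sided 5%. **Assumed, because the documents give neither:** ICC of 0.001, 0.005, 0.01 and 0.02, and receipt of whole blood by site type.

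**1. Reproduce the 90%.** With D events and whole-blood share p, power = Φ(√(D·p(1−p))·ln 1.9 − 1.96), where ln 1.9 = 0.642. Taking 11.1% as the overall rate, D = 892 × 0.111 = 99.0. At p = 0.5, √(99.0/4) × 0.642 = 3.19, so power = Φ(1.23) = 89.1%. This treats patients as independent.

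**2. Receipt follows site completely (upper bound on the loss).** The information D/4 is divided by the design effect (DEFF) = 1 + 148 × ICC. For example, ICC 0.01 gives DEFF 2.48, and √(99.0/4/2.48) × 0.642 = 2.03, so power = Φ(0.07) = 52.7%.

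**3. Mixed receipt.** The within-site part of the contrast is divided by 1 − ICC and the between-site part by DEFF. This is an approximation that relies on within-site comparisons.

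- 80% at whole-blood sites, 0% elsewhere: average within-site variance 0.16/2 = 0.08, between-site variance 0.4² = 0.16. Information = 99.0 × [0.08/(1 − ICC) + 0.16/DEFF].
- 80% v 20%: within-site 0.16, between-site 0.3² = 0.09. Information = 99.0 × [0.16/(1 − ICC) + 0.09/DEFF].

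| ICC (assumed) | DEFF | By site | 80% v 0% | 80% v 20% |
|---|---|---|---|---|
| 0 | 1 | 89.1% | 87.9% | 89.1% |
| 0.001 | 1.148 | 84.6% | 84.9% | 87.7% |
| 0.005 | 1.74 | 67.8% | 75.5% | 83.8% |
| 0.01 | 2.48 | 52.7% | 68.3% | 81.1% |
| 0.02 | 3.96 | 36.1% | 60.7% | 78.7% |

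**4. Take 11.1% as the control rate, as the assumption is worded.** Under proportional hazards the whole-blood rate is 1 − 0.889^HR.

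- Hazard 1.9 times lower on whole blood (the direction of Hypothesis #1A): rate 0.060, events 446 × (0.111 + 0.060) = 76.3, power 80.0% unclustered. At ICC 0.01 with exposure by site it is about 43%.
- Hazard 1.9 times higher: rate 0.200, events 138.9, power 96.6% unclustered. At ICC 0.01 with exposure by site it is about 67%.

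Neither gives 90% at N = 892. The sample size of 1,190 quoted for the secondary Aim 1 analyses, with the control-rate reading and the beneficial direction, gives 101.8 events and 89.9%, again without clustering.

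**5. Whole-blood share.** Three equal sites on each side imply 50%. At 33%, p(1−p) = 0.2211, and power with 99 events is 85.2% before any clustering.

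**The case against.** The strongest reply is that the loss is unknown and may be small. The analysis is by receipt, practice may change during the study, and sites may be added, so exposure may not be a site-level variable. With 80% v 20% receipt and ICC 0.001 the loss is little more than one percentage point. The planned model also already handles clustering, and enrolment is set by site volume. This stands, and it limits the point to the power statement. It does not supply the missing assumption.

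Three stronger readings are tempting, and the documents do not support them.

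- *The match at 89.1% proves that independence was assumed.* It does not. With 11.1% as the control rate and the higher-hazard direction, 138.9 events against about 102 needed for 90% leaves room for a DEFF of about 1.36 (ICC about 0.0024). All that can be said is that no allowance is listed.
- *The primary test is undefined, so the type I error is inflated.* An unadjusted log-rank test would reject a true null too often if sites differ, but only if it were read as the result, and the plan does not say that. The power assumptions name a Cox model, and Hypothesis#1A proceeds from the log-rank to the propensity-adjusted hierarchical Cox model for the independent effect. What is missing is a label. The hierarchical logistic model named under Subgroup Analysis occurs in an example and looks like a wording slip.
- *Site is in the Aim 1 propensity score and absorbs the exposure contrast.* The mention of site under Hypothesis#2A describes the blood-pressure score. Its reference back to Aim 1A may mean only the boosted-regression method. The text is ambiguous, and no more than that.

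**Conclusion.** The concern holds in a limited form: the 90% is not supported for the clustered analysis that the plan specifies. No single corrected power can be given. Over the assumed ICC range of 0.001 to 0.02 with 99 events and 1:1 sites, power runs from about 85% down to 36% if receipt follows site completely, and from about 88% down to 79% with 80% v 20% receipt. The 99 events rest on reading 11.1% as the overall rate, which is the reading that reproduces the claim at N = 892. On the control-rate wording the unclustered figure is already 80.0% in the hypothesised direction, or 96.6% in the other. A reader might infer that true power is near 50%; that would need both an ICC of about 0.01 and exposure fixed by site, and the documents establish neither. None of these figures includes propensity adjustment, which could lower the residual ICC or remove exposure information. The point should be fixed because it affects how the result is interpreted; it does not undermine the conduct of the study.

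**What to change.** Restate the power, or the detectable hazard ratio, in the Power Analysis section over a stated ICC range, for example 0.001 to 0.02. Alongside it give:

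- the assumed whole-blood share, reconciling 33% in Whole Blood Transfusion Sites with three equal sites on each side;
- assumed receipt of whole blood by site type;
- the direction of the hazard ratio of 1.9;
- the group to which 11.1% applies.

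As minor wording, label the whole-blood coefficient in the propensity-adjusted hierarchical Cox model as the primary test and the unadjusted log-rank as descriptive. Align the logistic wording under Subgroup Analysis, and state whether site enters the Aim 1 propensity score.

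The cost is a recalculation and some edits to the text, with a power figure that will probably be lower. No new data or added enrolment is needed.

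### The detectable odds ratios for the binary Hypothesis 1B outcomes are sized for an increase in events; in the hypothesised direction, 1.76 at a 10% control rate has about 74% power, not 90%

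*Combined protocol and SAP*

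**What the plan says.** In the Power Analysis section, the paragraph on Aim 1B secondary outcomes states: "For the binary outcomes, the odds ratio that can be detected is presented in Table 1". The table has one header, Event Rate, running from .1 to .6. The odds ratio row beneath it reads 1.76, 1.56, 1.49, 1.46, 1.46, 1.48. No direction is given. The only description of the header comes in the sentence on the hazard ratio row, which shares it: "the hazard ratio that can be detected over a range of event rates in the control group is also presented in Table 1".

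The settings follow at the end of the section: "For all secondary analyses, the type I error rate was set to 0.05, with a two-sided alternative hypothesis, and 90% power", and "For the Aim 1, the sample size will be 1,190".

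Hypothesis #1B is directional. Whole blood "will be associated with a lower incidence of 12 hour and 24 hour mortality, a lower incidence of death from exsanguination", and the same is predicted for multiple organ failure and nosocomial infection. The Analyses section lists these five as the binary outcomes.

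**The concern.** From a fixed control rate, an odds ratio and its reciprocal are not equally detectable. Below 50%, a reduction leaves fewer events and is harder to detect than an increase with the reciprocal odds ratio. A row of ratios above 1, read against control-group rates, describes harm from whole blood, whereas the hypothesis is benefit. A reader would naturally invert 1.76 and conclude that the study has 90% power for an odds ratio of 0.57 at a 10% control rate.

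The discrepancy is largest where events are rare. The plan takes control 4-hour mortality as 11.1%, and the Specific Outcome Definitions count exsanguination death only within the first 4 hours, so that outcome at least should sit near the low end of the table. A non-significant result there could be over-read as excluding a benefit that the study was not sized to detect.

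**Working it through.** **Inputs.** Two-sided alpha 0.05 (z = 1.960), 90% power and N = 1,190 come from the end of the Power Analysis. Equal groups of 595 are inferred from the assumptions list: "6 sites will be involved, three whole blood and three component sites" and "Each site will enroll 175 participants in 3.5 years of enrollment". Event rates and odds ratios are as printed.

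**Formulae.** With control rate p₁ and odds ratio OR, the other group's rate is p₂ = p₁·OR / (1 − p₁ + p₁·OR). With n per group and p̄ = (p₁ + p₂)/2:

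power = Φ{ ( |p₁ − p₂| − 1.960·√[2p̄(1 − p̄)/n] ) / √[(p₁(1 − p₁) + p₂(1 − p₂))/n] }

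**Step 1: reproduce the plan (10% column, increase).** p₂ = 0.176/1.076 = 0.1636. The difference is 0.0636, the pooled standard error 0.01961 and the unpooled 0.01952. Then (0.0636 − 1.960 × 0.01961)/0.01952 = 1.287 and power = 90.1%. Solving for exactly 90% power in every column:

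| Event rate | .1 | .2 | .3 | .4 | .5 | .6 |
|---|---|---|---|---|---|---|
| Printed OR | 1.76 | 1.56 | 1.49 | 1.46 | 1.46 | 1.48 |
| 90% power, increase | 1.758 | 1.557 | 1.487 | 1.460 | 1.459 | 1.482 |
| 90% power, reduction (1/OR) | 2.09 | 1.67 | 1.54 | 1.48 | 1.46 | 1.46 |
| 90% power, header read as average rate | 1.90 | 1.61 | 1.51 | 1.47 | 1.46 | 1.47 |

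Only the increase matches all six. The upturn to 1.48 at .6 also belongs to an increase; a reduction gives 1.46 there.

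**Step 2: same ratio, hypothesised direction (10% column).** OR = 1/1.76 = 0.568, so p₂ = 0.0568/0.9568 = 0.0594. The difference is 0.0406, with standard errors 0.01570 and 0.01566. Then (0.0406 − 1.960 × 0.01570)/0.01566 = 0.629 and power = 73.5%. The unpooled formula gives 73.7%, the Wald log-odds-ratio formula 72.6%, and simulation of the test 73.8%.

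**Step 3: all columns.**

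| Control rate | .1 | .2 | .3 | .4 | .5 | .6 |
|---|---|---|---|---|---|---|
| Rate after a reduction of the printed size | 5.9% | 13.8% | 22.3% | 31.3% | 40.7% | 50.3% |
| Power for that reduction | 73.5% | 81.3% | 85.3% | 87.7% | 90.1% | 91.9% |
| OR for a reduction with 90% power | 0.479 | 0.599 | 0.650 | 0.675 | 0.685 | 0.685 |

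Keeping 1/1.76 at a 10% control rate with 90% power would need 933 per group, 1,866 in total.

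**Step 4: sensitivity.** The Analyses section assigns these outcomes the same approach as Hypothesis 1A, which is a time-to-event analysis. A log-rank version of the first two contrasts gives 75% and 82%, so the conclusion does not depend on the two-proportion test.

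**The case against.** The strongest objection concerns the label. The odds ratio sentence does not say whose rate is tabulated; the control-group wording belongs to the hazard ratio. If the tabulated rate were the whole blood rate, 1.76 would compare 16.4% on component therapy with 10% on whole blood, which is the hypothesised benefit at 90% power. That reading is arithmetically possible. But both rows share one header, its only description is the control group, and the primary calculation also starts from a control event rate. If the sponsor did mean the whole blood rate, the header still needs correcting.

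It can also be said that nothing was miscalculated and that the test is two-sided. Both are true. However, a two-sided level controls false positives in both directions; it does not equalise power for an odds ratio and its reciprocal.

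Other points limit the size of the problem. From .3 upward the printed and corrected ratios differ little. The documents give no expected rates for 12- and 24-hour mortality, organ failure or infection, so only exsanguination death is tied by the text to a low rate. The row does not set the sample size, and the plan advises caution with secondary findings, though that general caution does not correct a stated figure.

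Finally, 1,190 and equal groups are themselves unsettled. The same section expects 892 consented patients, and the Whole Blood Transfusion Sites section says "WB sites will be selected based upon the ability to enroll 33% of patients for the overall cohort study". Power for the 10% v 5.9% contrast would be about 61% with 892 patients in equal groups, and about 66% with 1,190 patients and a 33% whole blood share. These points make the figures provisional; they do not restore the 90%.

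**Conclusion.** The concern holds. On the plan's own inputs the odds ratio row gives detectable increases from the tabulated rate. Read against control rates, as the text describes them, it overstates sensitivity to the hypothesised reduction at .1 to .4. The shortfall from 90% is about 16 percentage points at .1, 9 at .2, 5 at .3 and 2 at .4; there is none at .5, and the difference reverses slightly at .6.

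This rests on the event rate being the component-group rate, on 595 patients per group, and on an unadjusted comparison. None of the figures allows for clustering by site or propensity adjustment, so 74% should be read as a correction on the plan's own terms, not as the study's actual power.

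**What to change.** Replace the odds ratio row with detectable reductions. At N = 1,190, equal groups and 90% power these are 0.479, 0.599, 0.650, 0.675, 0.685 and 0.685 for control rates of .1 to .6. Settle the sample size and allocation first, and recompute the row at those values. Label the header as the event rate in the component (control) group and the ratio as whole blood versus component. If the printed row is kept, label it as the detectable increase in events.

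The cost is one table row and its labels. Patients, data and analyses are unchanged; the stated sensitivity at low event rates becomes less favourable.

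### The detectable effect of 0.13 given for continuous secondary outcomes has about 61% power at 1,190 patients and 49% at 892, not 90%, if it is a standardised mean difference

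*Combined protocol and SAP*

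**What the plan says.** The Power Analysis section treats the Aim 1B outcomes by type. For the continuous ones it gives a single figure: "For the continuous outcome, the effect size that can be detected is 0.13". The conditions come at the end of the same section: "For all secondary analyses, the type I error rate was set to 0.05, with a two-sided alternative hypothesis, and 90% power", and "For the Aim 1, the sample size will be 1,190".

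Earlier in that section the planned numbers are smaller: "we plan to initiate sampling on 1,050 patients over the enrollment time period of the study", and after an 85% consent rate, "we will consent for participation 892 patients for the study". The assumptions for the primary aim include "6 sites will be involved, three whole blood and three component sites", with the same enrolment at each site, which implies roughly equal groups. The paragraph on whole blood transfusion sites implies a different split: "WB sites will be selected based upon the ability to enroll 33% of patients for the overall cohort study".

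Under Analyses, Hypothesis#1B, the unadjusted comparison of continuous outcomes is described thus: "a two-sided t-test for correlated means will be used to compare the means between those receiving and not receiving whole blood". The next step is a hierarchical ANOVA, to account for clustering within institutions, with the propensity score as a model term. No matching of patients is described.

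**The concern.** The comparison is between two sets of different patients. For such a comparison, 1,190 patients in total is too few to detect a standardised difference of 0.13 with 90% power, so the figure fails on the plan's own inputs. This is separate from the question of whether 1,190, 1,050 or 892 is the right number.

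Transfusion ratios and transfusion requirements are named in Hypothesis 1B. A reader who takes the protocol at its word would expect a true difference of 0.13 to be missed one time in ten. At 892 patients it would be missed about half the time. That matters when a non-significant result on these outcomes is interpreted.

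**Working it through.** **Inputs from the plan.** Two-sided alpha 0.05 and 90% power (z values 1.960 and 1.282; unrounded sum 3.2415); N = 1,190 for Aim 1; 1,050 sampled and 892 consented; three whole-blood and three component sites (taken as 1:1), or 33% whole blood.

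**Assumption.** The effect size is an unadjusted difference in means divided by a common standard deviation. Clustering is left out at first, which favours the plan.

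**Step 1: try to reproduce 0.13.**
- Two independent groups of 595: 3.2415 × √(2/595) = 0.188. Not reproduced.
- Other readings at N = 1,190: 33:67 allocation 0.200; one-sided test 0.170; 80% power 0.162; Cohen's f (half of d) 0.094; one sample of 1,190 gives 0.094. None gives 0.13.
- Paired formula, 595 pairs, standardised by the SD of the within-pair differences: 3.2415/√595 = 0.1329, which rounds to 0.13.
- 1,190 patients in each arm: 3.2415 × √(2/1190) = 0.1329, the same number, because √(2/1190) = 1/√595.

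The figure can therefore be reproduced at the stated 90%, but only with pairs or with twice the stated total. A third route, 446 pairs (892/2) at 80% power, gives 0.1327.

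**Step 2: what independent groups can detect.** Detectable effect = 3.2415 × √(1/n1 + 1/n2). Power for 0.13 = Φ(0.13/√(1/n1 + 1/n2) − 1.960).

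| N and allocation | Detectable at 90% power | Power for 0.13 |
|---|---|---|
| 1,190, 1:1 | 0.188 | 61.1% |
| 1,050, 1:1 | 0.200 | 55.8% |
| 892, 1:1 | 0.217 | 49.3% |
| 1,190, 33:67 | 0.200 | 55.9% |
| 892, 33:67 | 0.231 | 44.7% |

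Worked example at 1,190, 1:1: √(4/1190) = 0.05798; 0.13/0.05798 = 2.242; 2.242 − 1.960 = 0.282; Φ(0.282) = 0.611. A noncentral t calculation at 1:1 gives 61.0% at 1,190 and 49.2% at 892.

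**Step 3: rounding.** Any value from 0.125 to 0.1349 prints as 0.13. Over that range, power at 1:1 is 58% to 64% at 1,190 and 46% to 52% at 892. Rounding does not close the gap.

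**Step 4: size of the gap in patients.** 90% power for 0.13 needs 2 × (3.2415/0.13)² = 1,244 per arm, or 2,488 in total.

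**Step 5: direction of the clustering effect.** Sites are chosen as whole-blood or component sites, so positive correlation within sites inflates the variance of the comparison. The documents give no intraclass correlation. As an illustration, assume 0.001 to 0.01 with 1,190/6 ≈ 198 patients per site. The design effect 1 + 197.3 × ICC is then 1.20 to 2.97, the detectable effect at 1,190 is 0.206 to 0.324, and power for 0.13 is about 54% to 25%.

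**The case against.** **The scale is undefined, and the final model is adjusted.** This stands as a condition on the result. The hierarchical model includes a propensity score, and adjustment can reduce residual variance. To bring 0.188 down to 0.13 at 1,190, covariates would have to explain 1 − (0.13/0.188)² ≈ 52% of the outcome variance. The plan states no such assumption.

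**The planned test is for correlated means, so a paired formula may have been intended.** A reader might infer that the authors assumed 595 matched pairs. The documents do not establish this: the calculation mentions no pairs, and 1,190 per arm yields the same number. Nor would a paired intention rescue the figure. The only correlation the plan names is within institutions. With 595 pairs and a raw-SD scale, a within-pair correlation of 0.5 would be needed to reach 0.1329, and none is stated.

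**These are secondary outcomes, and the plan urges caution in interpreting them.** This stands as to severity. The study is powered on 4-hour mortality, and 0.13 sets no sample size, enrolment target or decision rule. A reader might infer that null findings will be taken as ruling out an effect of 0.13; the plan contains no such rule. The caution concerns how findings are read, however, and does not correct a figure presented with 90% power.

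**Equal, independent, unclustered groups are themselves too favourable.** This also stands. The replacement figures must allow for the 33% share and be labelled as values before clustering.

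**Conclusion.** The stated pairing of 0.13 with 90% power is wrong if 0.13 is an unadjusted standardised mean difference, and the plan defines no other scale. On that reading, power is about 61% at 1,190 and 49% at 892 with equal groups, or 56% and 45% with 33% whole blood. The error is present at 1,190 itself, and no two-group reading tried at that total recovers the figure.

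The shortfall does not show that the study needs 2,488 patients, since nothing in the plan requires it to detect 0.13. It also does not touch the primary analysis. The effect of clustering is certain only in direction, and only to the extent that treatment follows site; its size depends on a correlation that the plan does not give. This is a planning figure that should be corrected, not a fault in the design.

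**What to change.** In the Power Analysis section, delete 0.13 and restate the effect detectable with 90% power for continuous Aim 1B outcomes:

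- equal independent groups: about 0.19 at 1,190 or 0.22 at 892;
- 33% whole blood: about 0.20 at 1,190 or 0.23 at 892.

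State the scale (a standardised mean difference, if that is meant), the N and the allocation used. Say that the values are best-case, before clustering within institutions, which lowers sensitivity further because treatment is largely set by site. If the sponsor did rely on pairing or on variance explained by covariates, the assumption should be written out with its value.

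The cost is a few lines of text and a less favourable stated sensitivity. No extra enrolment or design change is needed.
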